#### **6 STUDY INTERVENTION**

Study intervention is defined as any investigational intervention(s), marketed product(s), placebo, or medical device(s) intended to be administered to a study participant according to the study protocol.

Clinical supplies (MK-8189/placebo) will be packaged to support enrollment and replacement participants as required. When a replacement participant is required, the Sponsor or designee needs to be contacted before dosing the replacement participant. Clinical supplies will be affixed with a clinical label in accordance with regulatory requirements.

#### 6.1 Study Intervention(s) Administered

The study intervention(s) to be used in this study are outlined in Table 1.

#### Table 1Study Interventions

Arm Name	Arm Type	Inter- vention Name	Inter- vention Type	Dose Formu- lation	Unit Dose Strength(s)	Dosage Level(s)	Route of Admini- stration	Regimen/Treatment Period/Vaccination Regimen	Use	IMP/ NIMP	Sourcing
Active	Experi- mental	MK- 8189	Drug	Tablet	4 mg 12 mg	All dosage levels	Oral	Titrations 1, 2 and 3	Experi- mental	IMP	Provided centrally
Placebo	Placebo Compar- ator	Placebo	Drug	Tablet	0 mg	All dosage levels	Oral	Titrations 1, 2 and 3	Experi- mental	IMP	Provided centrally

IMP=investigational medicinal product; NIMP=noninvestigational medicinal product.

The classification of IMP and NIMP in this table is based on guidance issued by the European Commission and applies to countries in the EEA. Country differences with respect to the definition/classification of IMP/NIMP may exist. In these circumstances, local legislation is followed.

44

All supplies indicated in Table 1 will be provided per the "Sourcing" column depending on local country operational requirements. If local sourcing, every attempt should be made to source these supplies from a single lot/batch number where possible (e.g., not applicable in the case where multiple lots or batches may be required due to the length of the study, etc).

Refer to Section 8.1.8 for details regarding administration of the study intervention.

All placebos were created by the Sponsor to match the active product.

#### 6.2 Preparation/Handling/Storage/Accountability

#### 6.2.1 Dose Preparation

There are no specific calculations or evaluations required to be performed to administer the proper dose to each participant. The rationale for selection of doses to be used in this study is in Section 4.3.

#### 6.2.2 Handling, Storage, and Accountability

The investigator or designee must confirm appropriate temperature conditions have been maintained during transit for all study intervention received, and any discrepancies are reported and resolved before use of the study intervention.

Only participants enrolled in the study may receive study intervention, and only authorized site staff may supply or administer study intervention. All study interventions must be stored in a secure, environmentally controlled, and monitored (manual or automated) area in accordance with the labeled storage conditions with access limited to the investigator and authorized site staff.

The investigator, institution, or the head of the medical institution (where applicable) is responsible for study intervention accountability, reconciliation, and record maintenance (ie, receipt, reconciliation, and final disposition records).

For all study sites, the local country Sponsor personnel or designee will provide appropriate documentation that must be completed for drug accountability and return, or local discard and destruction if appropriate. Where local discard and destruction is appropriate, the investigator is responsible for ensuring that a local discard/destruction procedure is documented.

The study site is responsible for recording the lot number, manufacturer, and expiry date for any locally purchased product (if applicable) as per local guidelines unless otherwise instructed by the Sponsor.

The investigator shall take responsibility for and shall take all steps to maintain appropriate records and ensure appropriate supply, storage, handling, distribution, and usage of study interventions in accordance with the protocol and any applicable laws and regulations.

#### 6.3 Measures to Minimize Bias: Randomization and Blinding

#### 6.3.1 Intervention Assignment

Participants will be assigned randomly according to a computer-generated allocation schedule.

The sample allocation schedule is provided in Table 2.

Titration 1							
		Days 1-3	Days 4-28				
MK-8189 N=21		8 mg QD	16 mg QD				
Placebo	N=7	PBO	PBO				
	Titration 2						
		Days 1-3	Days 4-6	Days 7-28			
MK-8189	N=21	8 mg QD	16 mg QD	24 mg QD			
Placebo	N=7	PBO	PBO	PBO			
Titration 3							
		Days 1-3	Days 4-6	Days 7-9	Days 10-28		
MK-8189	N=21	4 mg QD	8 mg QD	16 mg QD	24 mg QD		
Placebo	N=7	PBO	PBO	PBO	PBO		
Note: The allocation scheduled will be stratified to AD participants with and without agitation-aggression							

Table 2	Sample	Allocation	Schedule
---------	--------	------------	----------

Note: The allocation scheduled will be stratified to AD participants with and without agitation-aggression and/or psychosis symptoms. Participants without agitation-aggression and/or psychosis symptoms will be assigned starting at the low allocation range and participants with agitation-aggression and/or psychosis symptoms (defined as a severity score of  $\geq 1$  and frequency score  $\geq 2$  on the NPI Agitation-Aggression and/or Hallucination and/or Delusion domains) will be assigned starting at the upper allocation range.

## 6.3.2 Stratification

Intervention allocation/randomization will be stratified according to the following factors:

1. participants with and without agitation-aggression and/or psychosis symptoms

For example, participants without agitation-aggression and/or psychosis symptoms will be assigned starting at the low allocation range and participants with agitationaggression and/or psychosis symptoms will be assigned starting at the upper allocation range. For this protocol agitation-aggression and/or psychosis symptoms are defined as a severity score of  $\geq 1$  and frequency score of  $\geq 2$  on the NPI Agitation-Aggression and/or Delusions and/or Hallucinations domains.

## 6.3.3 Blinding

A double-blinding technique with in-house blinding will be used. MK-8189 will be packaged identically to the matching placebo so that blind is maintained. The participant, the trial partner/caregiver, the investigator, and Sponsor personnel or delegate(s) who are involved in

the study intervention administration or clinical evaluation of the participants are unaware of the intervention assignments.

## 6.4 Study Intervention Compliance

- Interruptions from the protocol-specified treatment plan require consultation between the investigator and the Sponsor and written documentation of the collaborative decision on participant management.
- When participants self-administer study intervention(s) at home, daily phone calls will be made to check study intervention administration compliance. Compliance with study intervention will also be assessed at each subsequent visit by direct questioning and site review of the completed study intervention dosing diary as captured by the participant/trial partner/caregiver. In addition, compliance will be monitored via counting of returned tablets at selected CRU visits and documented in the source documents and eCRF. Deviation(s) from the prescribed dosage regimen should be recorded in the eCRF.
- A record of the number of MK-8189/placebo tablets dispensed to and taken by each participant must be maintained and reconciled with study intervention and compliance records. Intervention start dates, including dates for intervention delays and/or dose reductions will also be recorded in the CRF.
- When participants are dosed at the site, study intervention administration will be witnessed by the CRU staff. The staff will witness the participant/trial partner/caregiver record the dosing in the study intervention diary.

## 6.5 Concomitant Therapy

Concurrent use of any prescription or nonprescription medication, or concurrent vaccination during the ongoing study (i.e., after randomization or intervention allocation) must first be discussed between the investigator and Sponsor prior to administration, unless appropriate medical care necessitates therapy or vaccination should begin before the investigator and Sponsor can consult. The participant will be allowed to continue in the study if both the Sponsor and the investigator agree.

Acetaminophen and antacids (e.g., magnesium hydroxide) may be used for minor ailments without prior consultation with the Sponsor.

Moderate to strong inhibitors or inducers of CYP3A and moderate to strong inducers of CYP2C9 are not allowed as MK-8189 is being metabolized by these CYP enzymes and coadministration of inhibitors or inducers may potentially alter the metabolism and PK of MK-8189. See also Section 6.5.1 on rescue medication.

In addition, the following concomitant medications/vaccinations are permitted:

- Non-live vaccines may only be administered in consultation with the Sponsor.
- COVID-19 vaccine may be administered. Study intervention must be given at least 72 hours following or at least 48 hours prior to any COVID-19 vaccination.

Exception: Investigational COVID-19 vaccines (i.e., those not licensed or approved for Emergency Use) are not allowed.

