#### 6.6 **Dose Modification (Escalation/Titration/Other)**

The dose regimen for this trial is MK-8189 8mg/placebo Days 1-3 days followed by 16 mg/placebo Days 4-28 (Titration 1).

Following MK-8189/placebo treatment of approximately 8 participants for approximately 3 weeks, a decision will be made to continue dosing newly enrolled participants with the current regimen or modify to an alternate regimen. The following alternate treatment regimens may be explored during the study following a review of safety and tolerability data and a discussion with the investigators and the Sponsor. However, dose escalation above 16 mg will not occur without a review of PK data from the initial cohort of approximately 8 participants. Any change in the treatment regimen will be documented in a Protocol Clarification Letter.

- 8 mg/matched placebo Days 1-3, 16 mg/placebo Days 4-6 and 24 mg/placebo Days 7-28 (Titration 2)
- 4 mg/matched placebo Days 1-3, 8 mg/placebo Days 4-6, 16 mg/placebo Days 7-9 and 24 mg/placebo Days 10-28 (Titration 3)
- Other more conservative regimen

If medical care necessitates participants may:

- Skip a single dose and dosing may continue at the same dose level or adjusted downwards.
- Receive the same dose level to further explore safety and tolerability at that level.
- Receive a lower dose of the study intervention.
- Stop dosing.

Any change in dosing regimen will be documented in a Protocol Clarification Letter.

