# 7 DISCONTINUATION OF STUDY INTERVENTION AND PARTICIPANT WITHDRAWAL

## 7.1 Discontinuation of Study Intervention

Discontinuation of study intervention does not represent withdrawal from the study.As certain data on clinical events beyond study intervention discontinuation may be important to the study, they must be collected through the participant's last scheduled follow-up, even if the participant has discontinued study intervention. Therefore, all participants who discontinue study intervention before completion of the protocol-specified treatment regimen

will still continue to participate in the study as specified in Section 1.3 and Section 8.1.9, or per a PCL, if available.

Participants may discontinue study intervention at any time for any reason or be discontinued from the study intervention at the discretion of the investigator should any untoward effect occur. In addition, a participant may be discontinued from study intervention by the investigator or the Sponsor if study intervention is inappropriate, the study plan is violated, or for administrative and/or other safety reasons. Specific details regarding procedures to be performed at study intervention discontinuation are provided in Section 8.1.9.

A participant must be discontinued from study intervention, but continue to be monitored in the study, for any of the following reasons:

- The participant or participant's legally acceptable representative requests to discontinue study intervention.
- The participant's treatment assignment has been unblinded by the investigator, or through the emergency unblinding call center.
- The participant interrupts study intervention administration for more than 2 consecutive days or has 4 cumulative missed doses.
- The participant has a medical condition or personal circumstance which, in the opinion of the investigator and/or Sponsor, placed the participant at unnecessary risk from continued administration of study intervention.
- The participant has a positive UDS except for allowed concomitant medication administered during trial, at any time during the study. The drug screen can be confirmed by a recheck at the discretion of the investigator after discussion with the Sponsor.
- Any participant with EPS requiring treatment that is not or cannot be managed by down dosing.
- The participant no longer has a trial partner/caregiver or the trial partner/caregiver withdraws consent and a substitute cannot be identified.

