Discontinuation from study intervention is "permanent." Once a participant is discontinued from study intervention, they shall not be allowed to restart study intervention.

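### Does a COVID-19 vaccination allowed by Section 6.5 force permanent discontinuation under Section 7.1?

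*Combined protocol and SAP*

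**What the plan says.** Section 6.5 (Concomitant Therapy) covers any new medication or vaccination after randomization. Such use "must first be discussed between the investigator and Sponsor prior to administration, unless appropriate medical care necessitates therapy or vaccination should begin" before the two can consult. It adds: "The participant will be allowed to continue in the study if both the Sponsor and the investigator agree". COVID-19 vaccines, other than investigational ones, are then permitted with a timing condition: "Study intervention must be given at least 72 hours following or at least 48 hours prior to any COVID-19 vaccination".

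Section 7.1 (Discontinuation of Study Intervention) opens its list of mandatory reasons with "A participant must be discontinued from study intervention, but continue to be monitored in the study, for any of the following reasons". One item reads "The participant interrupts study intervention administration for more than 2 consecutive days or has 4 cumulative missed doses". The section also says "Discontinuation of study intervention does not represent withdrawal from the study", and then "Once a participant is discontinued from study intervention, they shall not be allowed to restart study intervention".

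Two other sections bear on interruptions. Section 6.4 requires the investigator and the sponsor to consult on any interruption and to document their joint decision. Section 6.6 lists what may be done if medical care requires it, including "Skip a single dose and dosing may continue at the same dose level or adjusted downwards". It lists no hold of several days.

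None of these sections says whether doses withheld because of Section 6.5 count toward the limits in Section 7.1.

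**The concern.** Dosing is once daily in the morning (Section 8.1.8.1). If every dose must fall either 48 hours or more before the vaccination or 72 hours or more after it, there is a dose-free window of 48 + 72 = 120 hours. That removes about five daily doses, while Section 7.1 acts on a third consecutive day or a fourth missed dose. Taken literally, one section allows an event and another ends treatment because of it.

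Discontinuation would then be permanent for a reason unrelated to safety. That participant's on-treatment safety follow-up and trough concentrations would be cut short in a study of up to about 28 people. Sites could also handle the same facts differently.

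**Working it through.** The plan gives no count of doses lost to a vaccination hold, so there is no figure to reproduce. The count can be made directly.

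**Inputs.** 28 daily doses, the last on Day 28 (Section 1.3); one morning dose (Section 8.1.8.1); the 48-hour and 72-hour limits (Section 6.5); the two limits in Section 7.1. Doses are assumed to be exactly 24 hours apart.

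**Rule for counting.** Let t(k) be the time of the Day k dose and v the time of vaccination.

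- Both sides observed: dose k is withheld if v − 48 < t(k) < v + 72.
- Only the 72-hour side observed (an unplanned vaccination): dose k is withheld if v < t(k) < v + 72.

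**Example.** Vaccination on Day 14, after that morning's dose, both sides observed. The first dose inside the window is Day 13 and the last is Day 17. Days 13, 14, 15, 16 and 17 are withheld, 5 doses.

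**Results.** Doses withheld if vaccination is before / exactly at / after that day's dosing hour:

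| Vaccination day | Both sides | 72-hour side only |
|---|---|---|
| 4 to 25 | 5 / 4 / 5 | 3 / 2 / 3 |
| 26 | 5 / 4 / 4 | 3 / 2 / 2 |
| 27 | 4 / 3 / 3 | 2 / 1 / 1 |
| 28 | 3 / 2 / 2 | 1 / 0 / 0 |

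If withheld doses count, the results compare with Section 7.1 as follows.

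- Both sides: a limit is reached throughout Days 4 to 27, and on Day 28 only before the morning dose.
- 72-hour side only: a limit is reached through Day 25 unless vaccination is exactly at the dosing hour, on Day 26 only before the morning dose, and not on Days 27 and 28.
- 48-hour side only: at most 2 doses are withheld, so no limit is reached.

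Day 3, at or after the morning dose, behaves like Day 4 (4 or 5 doses with both sides). On Days 1 and 2, and on Day 3 before the morning dose, the Day 1 dose itself lies in the two-sided window. The question there is when to start, not whether dosing was interrupted.

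**Doses lost only because restart is barred.** For vaccination on Day d after the morning dose, the last withheld dose is Day d + 3, leaving 28 − (d + 3) = 25 − d. At or before the dose, the last withheld dose is Day d + 2, leaving 26 − d. This applies only where a limit is reached.

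- Day 4: 21 or 22
- Day 14: 11 or 12
- Day 24: 1 or 2
- Day 25: 0 or 1
- Day 26 onward: 0

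**Do the two sections contradict each other?** Section 6.5 allows vaccination and says when a dose may be given. It does not promise that dosing resumes. A participant who is vaccinated, held, discontinued and monitored breaches neither section. Whether discontinuation is triggered depends on wording. The first limb of the Section 7.1 item makes the participant the one who interrupts, which need not cover a dose the protocol forbids. The second limb, on missed doses, names no actor and could cover it. Both readings are open.

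**Effect on the results.** One participant is 1/28 = 3.6% of the maximum planned enrollment. The target is at least 16 evaluable completers (Section 1.1), so 28 − 16 = 12 randomized participants could fail to complete before it is missed. Section 5.5 also allows replacement. Everyone who took one dose stays in the safety population (Section 9.5). The primary endpoints are adverse events and those leading to discontinuation. A discontinuation caused by a vaccination hold is not an adverse event and adds nothing to the second count if its reason is recorded correctly. There are no hypotheses, multiplicity adjustment or power calculation to disturb (Sections 9.8 and 9.9).

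**The case for a change.** The case for a change is a fair one. The limits in Section 7.1 are mandatory and no exemption can be found. Section 6.4 asks for consultation but waives nothing. The agreement in Section 6.5 concerns staying in the study, which Section 7.1 separates from staying on treatment. Section 6.6 speaks of one skipped dose. Section 8.10.7 allows changes such as a shorter duration, but ties them to newly available data and does not mention vaccination. The authors wrote an exception into another item of the same list, for a positive drug screen caused by allowed medication, so they knew how to exempt something. Even the narrower 72-hour reading usually reaches three days. A sentence in a Protocol Clarification Letter would cost nothing.

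The silence is real and the dose counts are correct. A clarifying sentence would do no harm.

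The rest is weaker. The timing rule is not emptied by Section 7.1: vaccination from 48 hours after the Day 28 dose costs no dose, and late in treatment barring restart costs none. The largest loss needs doses to be held for 48 hours beforehand, so it needs a planned vaccination. That is the case the sponsor normally hears of first and may be able to have rescheduled. An unplanned vaccination withholds at most 3 doses. The proposed sentence would record an answer without any statistical ground for preferring one, since the choice is clinical.

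**Conclusion.** No change to the plan is called for. Sections 6.5 and 7.1 do not cross-refer, and the protocol leaves open whether a hold it imposes counts as an interruption or a missed dose. That is a missing detail of interpretation. If a case arises, Sections 6.4 and 6.5 already bring it to the investigator and the sponsor, and Section 6.4 requires their decision on the interruption to be documented. How the two sections are reconciled is for the sponsor, and no view on it is taken here.

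If both sides are observed, 3 to 5 doses are withheld for a vaccination on Days 4 to 27. If only the 72-hour side is observed, at most 3 are withheld. If the hold counts, the bar on restart adds 21 or 22 lost doses at Day 4 and none from Day 26. This rests on exact 24-hour dosing and on reading the *or* in Section 6.5 dose by dose. The number of participants affected is unknown and may be zero. Under either reading the descriptive safety summary stays sound, because earlier data are kept, monitoring continues and replacement is available.

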#### **Continued Medication Use**

Participants may continue treatment with their prescribed cholinesterase inhibitors, memantine and aducanumab for the treatment of AD during the trial. The prescribed dose and regimen of medication must be stable for at least 3 months prior to screening and there are no expected changes in co-medication during the study.

In addition, medications to treat mild chronic conditions such as hypothyroidism, diabetes, high blood pressure, chronic respiratory conditions or other medical conditions are allowed during the study. For permitted medications, the prescribed dose and regimen of medication must be stable for at least 2 months prior to screening and there are no expected changes in co-medication during the study.

A participant's continued use of medications that may cause somnolence, including but not limited to benzodiazepines and sedating antihistamines, must be discussed between the investigator and the Sponsor prior to MK-8189 administration.

## 6.5.1 Rescue Medications and Supportive Care

If over the course of the study behavioral symptoms worsen, if medically appropriate, the participant may be administered quetiapine 50 mg.

#### 6.6 **Dose Modification (Escalation/Titration/Other)**

The dose regimen for this trial is MK-8189 8mg/placebo Days 1-3 days followed by 16 mg/placebo Days 4-28 (Titration 1).

Following MK-8189/placebo treatment of approximately 8 participants for approximately 3 weeks, a decision will be made to continue dosing newly enrolled participants with the current regimen or modify to an alternate regimen. The following alternate treatment regimens may be explored during the study following a review of safety and tolerability data and a discussion with the investigators and the Sponsor. However, dose escalation above 16 mg will not occur without a review of PK data from the initial cohort of approximately 8 participants. Any change in the treatment regimen will be documented in a Protocol Clarification Letter.

- 8 mg/matched placebo Days 1-3, 16 mg/placebo Days 4-6 and 24 mg/placebo Days 7-28 (Titration 2)
- 4 mg/matched placebo Days 1-3, 8 mg/placebo Days 4-6, 16 mg/placebo Days 7-9 and 24 mg/placebo Days 10-28 (Titration 3)
- Other more conservative regimen

If medical care necessitates participants may:

- Skip a single dose and dosing may continue at the same dose level or adjusted downwards.
- Receive the same dose level to further explore safety and tolerability at that level.
- Receive a lower dose of the study intervention.
- Stop dosing.

Any change in dosing regimen will be documented in a Protocol Clarification Letter.

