#### 4 STUDY DESIGN

#### 4.1 Overall Design

This is a randomized, placebo-controlled, parallel-group, multisite, double-blind study of MK-8189 in participants with Alzheimer's Disease with and without neuropsychiatric symptoms. To most closely simulate the patient population for the indication evaluated, it is preferred that participants included in this study have symptoms of agitation-aggression or psychosis (defined as a severity of score  $\geq 1$  and frequency score of  $\geq 2$  on the NPI Agitation-Aggression and/or Delusions and/or Hallucinations domains).

Up to approximately 28 participants will be enrolled to ensure at least 16 participants complete the study. Note: Greater than 16 participants may be required to complete the study if additional study data are needed to further understand the safety and tolerability profile of MK-8189 in the AD population.

This is an outpatient study as participants will be dosing at home and will require visits to the CRU per the SoA. Therefore, participants must have a trial partner/caregiver as described in the inclusion/exclusion criteria.

The first 8 participants will be randomized to receive MK-8189 8 mg/placebo QD Days 1-3, 16 mg/placebo QD Days 4-28 (Titration 1). Participants may be down-titrated by the investigator at any time without consultation of the Sponsor in the case of safety or tolerability issues. Changes in the dosage regimen will be communicated to the Sponsor and the Sponsor will document changes in a Protocol Clarification Letter. After approximately 8 participants have completed approximately 3 weeks of dosing, AE data will be reviewed to determine whether to continue to enroll participants at the Titration 1 regimen or whether participants should receive an alternate dosing regimen (e.g., MK-8189 8 mg/placebo QD Days 1-3, 16 mg/placebo QD Days 4-6, 24 mg/placebo Days 7-28 (Titration 2) OR MK-8189 4 mg /placebo QD Days 1-3, 8 mg/placebo Days 4-6, 16 mg Days 7-9, 24 mg Days 10-28 (Titration 3)). Prior to initiation of an alternate regimen that includes escalation to a dose above 16 mg, the PK data from the initial cohort of participants will be required to be reviewed. The decision will be made jointly between the investigators and the Sponsor and any change to the dosing regimen will be documented in a Protocol Clarification Letter. See section 6.6 for allowed dose modifications.

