### 4.3 Justification for Dose

Currently the efficacious dose of MK-8189 is unknown, however, based on data from in vivo preclinical assays (see Section 2.1 and the IB), enzyme occupancy of 30% is expected to be required for efficacy in neuropsychiatric symptoms associated with dementia. A dose of 8 mg is expected to result in a mean C24 (90% confidence interval) enzyme occupancy of approximately 40% (34, 47). Proof of concept has been established for 12 mg of MK-8189 in schizophrenia patients (P005), however, doses up to and including 24 mg are being evaluated in a Phase 2b study (P008) to understand if greater efficacy is observed with higher doses. Recent literature suggests that for antipsychotics to be effective in the treatment of behavioral symptoms associated with dementia, doses may need to be similar to those used for the treatment of schizophrenia [Grossberg, G. T., et al 2020]. Preliminary PK data from P011 suggest the median C24 value in healthy elderly following multiple doses of MK-8189 16 mg will be similar to that observed following multiple 24 mg doses of MK-8189 in non-elderly adults with schizophrenia. Therefore, the initial titration regimen in the current study will escalate MK-8189 doses up to 16 mg. If multiple doses of MK-8189 16 mg is generally well tolerated in the initial cohort of ~8 participants and, based on a PK analysis of these participants, MK-8189 exposure is less than anticipated and thus closer to exposures observed in younger (< 60 years of age) adult participants, an alternate titration regimen escalating to 24 mg of MK-8189 (Titration Regimen 2) may be explored.

As this is a Phase 1 assessment of MK-8189 in humans, and the PK, pharmacodynamic and safety profiles of the compound are still being evaluated, modifications to the dose or dosing regimen may be required to achieve the scientific goals of the study objectives and/or to ensure appropriate safety monitoring of the study participants. Details of allowed modifications are provided in Section 8.10.7.

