## 8.10.7 Study Design/Dosing/Procedures Modifications Permitted Within Protocol Parameters

See Section 6.6 for Dosing modifications permitted per protocol.

This is a Phase 1 assessment of MK-8189 in humans, and the PK, pharmacodynamic, and safety profiles of the compound are still being elucidated. This protocol is written with some flexibility to accommodate the inherent dynamic nature of Phase 1 clinical studies. Modifications to the dose, dosing regimen, and/or clinical or laboratory procedures currently outlined may be required to achieve the scientific goals of the study objectives and/or to ensure appropriate safety monitoring of the study participants.

As such, some alterations from the currently outlined dose and/or dosing regimen may be permitted based on newly available data, but the maximum daily dose may not exceed those currently outlined in the protocol.

- Repeat of or decrease in the dose and/or titration steps of the study intervention administered.
- Decrease in the duration of study intervention administration (e.g., number of days).
- Addition of PK pause.
- Instructions to take study intervention with or without food or drink may also be modified based on newly available data.
- Modification of the PK sample processing and shipping details based on newly available data.

The PK sampling scheme currently outlined in the protocol may be modified during the study based on newly available PK or pharmacodynamic data (e.g., to obtain data closer to the time of peak plasma concentrations). If indicated, these collected samples may also be assayed in an exploratory manner for metabolites and/or additional pharmacodynamic markers.

Up to an additional 50 mL of blood may be drawn for safety, PK, and/or pharmacodynamic analyses. The total blood volume withdrawn from any single participant will not exceed the maximum allowable volume during his/her participation in the entire study (Appendix 8).

The timing of procedures for assessment of safety procedures (e.g., vital signs, ECG, safety laboratory tests, etc.) may be modified during the study based on newly available data. Additional laboratory safety tests may be added to blood samples previously drawn to obtain additional safety information. These changes will not increase the number of study procedures for a given participant during his/her participation in the entire study.

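### Do Sections 4.1, 4.3 and 6.6 conflict on what must be shown before a regimen goes above 16 mg?

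*Combined protocol and SAP*

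**What the plan says.** Section 4.1 sets the sequence. After about 8 participants have had about 3 weeks of dosing, "AE data will be reviewed to determine whether to continue to enroll participants at the Titration 1 regimen" or move to an alternate regimen. Titrations 2 and 3 are offered there as examples, and both end at 24 mg. "Prior to initiation of an alternate regimen that includes escalation to a dose above 16 mg", the first cohort's PK data must be reviewed. Investigators and Sponsor decide jointly, and any change is recorded in a Protocol Clarification Letter.

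Section 6.6 repeats the procedure ("dose escalation above 16 mg will not occur without a review of PK data from the initial cohort of approximately 8 participants") and lists Titration 2, Titration 3 and a further, unspecified more conservative option.

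Section 4.3 gives the reasoning. If 16 mg is generally well tolerated in the first cohort and "MK-8189 exposure is less than anticipated and thus closer to exposures observed in younger (< 60 years of age) adult participants", then "an alternate titration regimen escalating to 24 mg of MK-8189 (Titration Regimen 2) may be explored". Titration 3 is not mentioned.

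Section 4.2 covers the downward direction: tolerability problems in the first 8 lead to a more conservative regimen for the rest.

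The cross-references run towards 6.6. Section 4.3 says "Details of allowed modifications are provided in Section 8.10.7", Section 8.10.7 says "See Section 6.6 for Dosing modifications permitted per protocol", and Section 4.1 says "See section 6.6 for allowed dose modifications". Section 6.6 does not point back to 4.3, although 6.2.1 names 4.3 as the source of the dose rationale.

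Section 9.7 provides for descriptive summaries, as needed, to support decision meetings. It names safety labs, vital signs and ECGs, and excludes individual-level results.

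**The concern.** A reader who follows the cross-references ends at 6.6, which requires reviews but states no finding they must produce. A reader who starts at 4.3 finds two. The same first-cohort data could then seem to support different decisions. Titration 3 adds to the doubt: it is covered by the PK review but absent from 4.3, and the wording of the last option in 6.6 could suggest that Titration 3 is itself one of the more conservative regimens, although it reaches 24 mg. Section 9.7 also omits the two kinds of data on which 4.1 and 6.6 rest the decision, and adverse events are the primary endpoint (Section 9.4).

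What would be at stake is exposure to 24 mg in an elderly population with dementia, in a study with no data monitoring committee (Synopsis) and no prespecified criteria for early termination (Section 4.4.1).

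**Working it through.** There is no stated figure to reproduce: Section 9.9 gives no power calculation and Section 9.3 no hypothesis. The check is to set the sections side by side, with some arithmetic on what a move to 24 mg would involve.

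**The two findings in 4.3.** Each can be present or absent, giving 2 × 2 = 4 first-cohort outcomes.

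| 16 mg tolerated | Exposure below expectation | 4.3 | 4.2 | 4.1 and 6.6 |
|---|---|---|---|---|
| yes | yes | supports exploring 24 mg | not engaged | reviews, then joint decision |
| yes | no | findings not met | not engaged | reviews, then joint decision |
| no | yes | findings not met | more conservative regimen | reviews, then joint decision |
| no | no | findings not met | more conservative regimen | reviews, then joint decision |

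The first row agrees across sections. The last two are directed by 4.2. They become doubtful only if a regimen ending at 24 mg is taken to be more conservative than one ending at 16 mg, which the text does not say. The second row is the one clear gap. Even there 4.3 is permissive and not exclusive, and the mandatory PK review looks at exactly the quantity that separates row 1 from row 2. To count rows 2 to 4 as conflicts, one must read the silence of 4.1 and 6.6 as permission and set 4.2 aside.

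**Why the PK finding has content.** Section 2.2.2 reports C24 about 50% higher in healthy elderly participants than in non-elderly adults, and exposure roughly proportional to dose from 2 to 48 mg. Then 16 mg × 1.5 = 24 mg, which agrees with the comparison in 4.3. By the same ratio 24 mg × 1.5 = 36 mg. If participants with Alzheimer's disease resemble healthy elderly people, 24 mg corresponds to about 36 mg in non-elderly adults. If they resemble elderly participants with schizophrenia, it corresponds to about 24 mg. The PK review is where that question is settled, whichever section is open on the desk.

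**What would follow a move to 24 mg.**
- Days at 24 mg, Titration 2: 28 − 7 + 1 = 22, and 22/28 = 79%.
- Days at 24 mg, Titration 3: 28 − 10 + 1 = 19, and 19/28 = 68%.
- Participants enrolled after the decision: 16 − 8 = 8 (if all of the first 8 complete and the study stops at 16 completers) up to 28 − 8 = 20.
- On active drug at 21/28 = 0.75: 8 × 0.75 = 6 up to 20 × 0.75 = 15.

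These figures describe exposure if a 24 mg regimen is opened. They do not measure the misalignment between sections.

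**Section 9.7.** The list describes summaries prepared as needed; it does not say that nothing else may be reviewed. Section 4.1 already mandates the AE review, and 4.1 and 6.6 the PK review. A longer list is not free either. If 3:1 holds in the first 8 (the documents do not say it does), the cohort has 8 × 0.75 = 6 active and 2 placebo participants. The C24hr statistics in 9.6 include minimum and maximum, which at that size are two people's values, while 9.7 bars individual results. AE tables by arm with 2 placebo participants could reveal assignments to investigators who are blinded (Section 6.3.3) and share the decision (Section 4.1).

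**Effect on the analysis.** Section 9.6 tabulates adverse events descriptively, 9.5 reports participants by treatment actually received, and 9.8 makes no multiplicity adjustment because nothing is tested. No error rate or estimate depends on how the regimen decision is worded.

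**The case for a change.** The best case for a change is that 6.6 is the operative section, since 4.1 and 8.10.7 both send the reader there, yet it omits the only findings the protocol states. With no monitoring committee, and with letters on protocol alterations reaching the ethics committee only at the investigator's discretion (Section 8.10.7), the written rule carries much of the control. Declared Phase 1 flexibility does not explain why one section states findings and another leaves them out. A pointer from 6.6 to 4.3 would cost one line.

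Part of this stands. Row 2 of the table is open, and the status of Titration 3 against both 4.3 and 4.2 is not stated. Those passages need one agreed reading from the sponsor's clinical team. What does not stand is the step from there to a defective rule. No sentence in one section forbids what another requires. The Sponsor shares the decision and is bound by the whole protocol, 4.3 included. The PK review applies to every regimen above 16 mg, so Titration 3 does not escape it. The starting-dose and maximum-dose limits (4.3.1, 4.3.2), down-titration at any time (4.1) and the discontinuation rules (7.1) also hold on any reading.

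**Conclusion.** No change to the plan follows. The text is a rationale in 4.3 and a procedure in 4.1 and 6.6 that lack a link. A team applying all the sections would review adverse events and PK, weigh them against the two findings in 4.3, and follow 4.2 if tolerability is poor. The misalignment amounts to one of four outcomes left clearly open and one regimen whose status is unstated. Any regimen change must already be documented in a Protocol Clarification Letter, which gives the clinical team a place to record the reading it adopts. Which reading that should be is not a statistical matter.

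The conclusion rests on two assumptions: that those deciding read 4.2 and 4.3 together with 6.6, and that the list in 9.7 is not meant to exclude data whose review other sections require. Nothing in the documents points against either.
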